8.0 DRUG/TREATMENT INFORMATION

8.1 Cisplatin

- Other names for the drug(s): Platinol
- Classification - type of agent: Cytotoxic chemotherapy
- Mode of action: The dominant mode of action of cisplatin appears to be inhibition of the incorporation of DNA precursors, although protein and RNA synthesis are also inhibited. Although this drug seems to act as an alkylating agent, there are data to indicate that its mode and sites of action are different from those of nitrogen mustard and the standard alkylating agents.
- Storage and stability: Please refer to the cisplatin prescribing information for storage and stability of the cisplatin commercial product
- Protocol dose: Weekly
- Preparation: Please refer to the cisplatin prescribing information for storage and stability of the cisplatin commercial product.
- Route of administration for this study: Intravenous
- Incompatibilities: Cisplatin may interact with metal aluminium to form a black precipitate of platinum. All aluminium-containing IV sets, needles, catheters and syringes should be avoided. There is a total loss of cisplatin in 30 minutes at room temperature when mixed with metoclopramide and sodium metabisulphite in concentrations equivalent to those that would be found on mixing with a commercial formulation of metoclopramide. Cisplatin and sodium bisulphite have been known to react chemically. Such antioxidants might inactivate cisplatin before administration if they are present in intravenous fluids.
- Availability: Commercially available
- Side effects: Human toxicity includes nausea, vomiting, renal toxicity (with an elevation of BUN and creatinine and impairment of endogenous creatinine clearance, as well as renal tubular damage, which appears to be transient), ototoxicity (with hearing loss that initially is in the high-frequency range, as well as tinnitus), and hyperuricemia. Much more severe and prolonged toxicity has been observed in patients with abnormal or obstructed urinary excretory tracts. Myelosuppression, often with delayed erythrosuppression, is expected. Please see the package insert for a comprehensive list of adverse events.
- Nursing implications: Not applicable

8.1.1 Return and Retention of Study Drug Not applicable

9.0 STATISTICAL CONSIDERATIONS

9.1 Study Design/Study Endpoints

9.1.1 Study design:

Phase I Rolling 6 design with dose expansion cohort
 Study design will be a rolling 6 dose escalation study, a modification to the standard 3 + 3 design (29). In contrast to the 3 + 3 design where patients are enrolled in cohorts of 3, the rolling 6 design allows for continuous enrollment up to a total of 6 patients at the same dose level. The dose level assigned to a new patient is based on the number of patients currently enrolled and evaluable, and the number of patients experiencing a DLT. Once six patients have been enrolled at the current dose level, enrollment will stop until at least 5 of the 6 patients have completed evaluation for DLT. Escalation to the next dose level occurs if at time of enrollment 3/3, 4/4, 5/5, 5/6, or 6/6 patients at the dose level are evaluated for and without DLT. De-escalation occurs if at the time of enrollment, 2 or more patients have experienced a DLT at the dose level.

DLT definition:

- Any CTCAE grade 4 toxicity (generally described as life-threatening consequences with urgent intervention indicated) attributed to RT during and up to 3 months post-treatment
- Persistent CTCAE grade 3 mucositis at 3 months post-treatment
 - CTCAE definitions:
 - Oral mucositis: severe pain; interfering with oral intake
 - Pharyngeal mucositis: severe pain; unable to adequately aliment or hydrate orally; limiting self-care ADL
 - To decrease subjectivity of interpretation by each clinician, the definition for grade 3 mucositis was consolidated as below:
 - Severe pain defined as needing daily opioid use of >30 morphine equivalent dose during the past week for mucositis, AND
 - The pain interferes with oral intake or swallowing defined as tolerating a liquid only diet or requiring tube feeds (with the exception of patients who were on a liquid only diet at baseline prior to RT, in which case they would need to be feeding tube dependent to satisfy this definition).

MTD definition: highest dose/fractionation level among those listed in section 4.1.2 at which ≤ 1 of 6 patients have experienced a DLT.

During the dose expansion phase, patients will be enrolled at MTD to reach the total accrual goal of 24 patients.

9.1.2 Primary endpoint

- MTD of HFRT

9.1.3 Secondary endpoints

- Physician-reported acute and late toxicities
 - Rate of \geq grade 3 acute toxicities during treatment, and at 1 and 3 months after treatment using CTCAE v5.0
 - Rate of \geq grade 3 late toxicities at 6 and 12 months after treatment using CTCAE v5.0
- Oncologic outcomes: LRC, PFS, and OS from start of treatment
- Patient-reported QOL:

- MDADI, UW-QOL, and EQ-5D-5L scores at baseline, 1, 3, 6, and 12 months after treatment
- Feeding tube dependence rate at baseline, 1, 3, 6, and 12 months after treatment

9.2 Sample Size and Accrual

We anticipate 3-6 patients in each cohort with a maximum of 12 total patients (e.g. 6 in level 0, 6 in level 1 or -1) during the Rolling 6 dose escalation phase.

During the dose expansion phase, patients will be accrued until a total sample size of 24 is reached to ensure at least 20 evaluable patients at 1 year assuming an attrition rate of 15%. We anticipate accruing 3 patients per month for a total accrual period of approximately 3 years accounting for time to reach the primary endpoint at 3 months prior to enrolling on to the next cohort.

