RO-APM	Radiation Oncology-Alternative Payment Model
ROSAC	Radiation Oncology Safety Assurance Committee
RT	Radiation Therapy
SAE	Serious Adverse Event
SCCC	Simmons Comprehensive Cancer Center
SD	Stable Disease
UPIRSO	Unanticipated Problems Involving Risks to Subjects or Others
UTSW	University of Texas Southwestern Medical Center
UW-QOL	University of Washington Quality of Life Questionnaire
VMAT	Volumetric Modulated Arc Therapy

STUDY SCHEMA

STUDY SUMMARY

Title	HYHOPE: Phase I study of de-intensified hypofractionated radiation therapy for human papilloma virus-associated oropharynx cancer
Short Title	HYHOPE: De-intensified hypofractionated radiation therapy for HPV-associated oropharynx cancer
Protocol Number	STU 2020-1079
Phase	Phase I
Methodology	Rolling 6 dose finding cohort followed by dose expansion cohort
Study Duration	3 years to accrue, additional 1 year of follow-up
Study Center(s)	Single-center
Objectives	To assess the maximum tolerated dose/fractionation and signal for efficacy of de-intensified hypofractionated radiotherapy for favorable HPV-associated oropharynx cancer
Number of Subjects	24
Diagnosis and Main Inclusion Criteria	T1-3 (≤ 6 cm), N0-2 (except T1-2N0) p16 positive oropharyngeal squamous cell carcinoma with ≤ 10 pack-year smoking history
Study Product(s), Dose, Route, Regimen	Hypofractionated intensity modulated radiotherapy with concurrent chemotherapy (weekly cisplatin)
Duration of administration	3-4 weeks
Reference therapy	Conventionally fractionated radiotherapy (60-70 Gy) over 6-7 weeks with concurrent chemotherapy (historical control)
Statistical Methodology	Phase I: standard rolling 6 design to determine the maximum tolerated dose/fractionation. Additional patients will be enrolled to reach 24 patients to achieve 20 evaluable patients for the clinical response endpoint assuming a 15% attrition rate.

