7.5 Stopping Rules

The primary hypothesis of the phase 1 study is that de-intensified HFRT is safe and tolerable. The trial will terminate during the rolling 6 dose escalation phase if it has reached level -1 and 2 patients experience dose limiting toxicity (DLT) at this dose level.

The secondary hypothesis is that the crude 1-year LRC rate is at least 85% (based on historical controls). In other words, for the target of 20 evaluable patients at 1 year, up to 3

patients can have a LRR and satisfy the pre-specified hypothesis. Thus, if a 4th patient enrolled on the trial experiences LRR within 1 year of completing the study treatment, the trial will be terminated for futility.

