9.3.2 Secondary endpoints

9.3.2.1 Locoregional control

LRC will be analyzed based on the definition in section 6.2 and estimated using cumulative incidence statistics, with death serving as a competing risk.

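### Twenty-four patients give an expected 20 evaluable at 1 year rather than ensuring it, and the limit of 3 recurrences matches 85% control only at 20 or more evaluable (minor)

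*Combined protocol and SAP*

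**What the plan says.** - **Section 9.2 (Sample Size and Accrual):** in the expansion phase "patients will be accrued until a total sample size of 24 is reached", and the reason given is "to ensure at least 20 evaluable patients at 1 year assuming an attrition rate of 15" percent.
- **Section 7.5 (Stopping Rules):** the secondary hypothesis is that "the crude 1-year LRC rate is at least 85% (based on historical controls"). The plan converts this to a count: "for the target of 20 evaluable patients at 1 year, up to 3" patients may recur. A 4th LRR among enrolled patients within 1 year of completing treatment ends the trial for futility.
- **Section 9.3.2.1 (Locoregional control):** LRC is "estimated using cumulative incidence statistics, with death serving as a competing risk". Section 9.1.3 dates LRC from the start of treatment.
- **Study Summary, Statistical Methodology:** the same 24 patients are enrolled "to achieve 20 evaluable patients for the clinical response endpoint assuming a 15% attrition rate". Clinical response is not among the endpoints in 2.3 or 9.1.3.
- **Section 4.8 (Subject Replacement):** patients who do not complete radiotherapy for reasons unrelated to toxicity may be replaced. Nothing provides for patients lost after radiotherapy.

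**The concern.** The 85% figure is the only quantified efficacy criterion in the protocol, and the expansion cohort is sized to judge it. Two features make that judgement less firm than it reads.

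First, an average of just over 20 evaluable patients is presented as a guarantee, while the count derived from it has no slack: 17 of 20 is exactly 85%. No section says how 3 LRRs should be read if fewer than 20 are evaluable.

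Second, the hypothesis is framed as a crude rate in evaluable patients, but LRC will be estimated by a time-to-event method with a different starting point. The plan does not say which figure decides whether 85% was met. What is at stake is the interpretation of a borderline efficacy result, not patient safety or the primary endpoint.

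**Working it through.** **Inputs.** N = 24, target 20 evaluable, attrition 15% (9.2); benchmark 85% and limit 3 (7.5). Assumed, because the plan is silent: patients drop out independently, no one is replaced, and LRR is independent of attrition.

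**1. Reproduce the plan's size.** 20 / (1 − 0.15) = 23.53, rounded up to 24. The plan's figure is reproduced. Expected evaluable = 24 × 0.85 = 20.4.

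**2. Chance of reaching 20.** With X ~ Binomial(24, 0.85), P(X ≥ 20) = 0.713, so P(X < 20) = 0.287. Of that shortfall, 0.147 is at 19 and 0.082 at 18, so 0.229 of the 0.287 lies within two patients of the target. Sensitivity: P(X ≥ 20) = 0.915 at 10% attrition and 0.460 at 20%.

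**3. Count against rate.** Observed LRC with k LRRs in m evaluable is 1 − k/m.

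| Evaluable m | LRC with 3 LRRs | LRC with 4 LRRs | Most LRRs giving at least 85% |
|---|---|---|---|
| 17 | 82.4% | 76.5% | 2 |
| 18 | 83.3% | 77.8% | 2 |
| 19 | 84.2% | 78.9% | 2 |
| 20 | 85.0% | 80.0% | 3 |
| 24 | 87.5% | 83.3% | 3 |

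At most 2 LRRs are compatible with 85% for m = 14 to 19, and at most 3 for m = 20 to 24. Four LRRs give at most 83.3% for any m up to 24.

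**4. How often count and rate would disagree.** This needs fewer than 20 evaluable and exactly 3 LRRs: the sum over m < 20 of P(X = m) × P(3 LRRs among m).

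| True LRR rate | Joint probability |
|---|---|
| 5% | 1.4% |
| 10% | 4.9% |
| 15% | 6.9% |

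**5. Crude rate against cumulative incidence.** Take 24 treated, no deaths, LRRs at 3 and 6 months, 5 patients lost just after the 6-month LRR, and an LRR at 9 months.
- Crude: 24 − 5 = 19 evaluable, 3 LRRs, 16/19 = 84.2%.
- Time-to-event: 24 − 2 − 5 = 17 at risk at 9 months, so LRC = (23/24)(22/23)(16/17) = 86.3%.

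The same data fall on opposite sides of 85%. If all 5 losses came before the first LRR, the estimate would be (18/19)(17/18)(16/17) = 16/19 = 84.2%, equal to the crude rate. The discordance therefore depends on the loss pattern.

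**6. Time origin.** Section 7.5 counts from completion of treatment and 9.1.3 from its start. Radiotherapy lasts 3–4 weeks (4.5), so 12 months from the start falls about 11 months after completion. The last scheduled visit is 12 months after completion, plus or minus 4 weeks (5.3). An LRR found at an on-time final visit counts under 7.5 but falls outside a 12-month estimate dated from the start.

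**The case against.** The strongest reply is that nothing has been miscalculated. Twenty-four is the usual inflation, and the fault lies in one word. Section 7.5 states the hypothesis as a rate and ties the count to the target of 20; it never claims that 3 of 19 meets 85%. The only unconditional count is the futility stop at the 4th LRR, and with 24 or fewer patients that stop cannot contradict the benchmark. At 3 LRRs in 19 the trial simply continues, which is no declaration of success. A crude count for monitoring beside cumulative incidence for final estimation is ordinary practice, and the plan states no test, alpha or power for LRC. Section 4.8 could also lift the 71% if replacements come on top of the 24.

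Most of this stands, and it limits the point. What it leaves open is that 9.2 does promise at least 20, that optional replacement does not reach losses between the end of radiotherapy and 1 year, and that the plan names no governing estimator or time origin for the 85% judgement.

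A reader might infer from the 28.7% shortfall that count and hypothesis conflict in more than a quarter of trials. The figures do not support that: 28.7% is only the chance of being where a conflict is possible, and an actual conflict also needs exactly 3 LRRs (step 4).

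**Conclusion.** The point holds as a minor one. Accrual of 24 is right as an expected-value calculation but does not ensure 20 evaluable. The limit of 3 LRRs is equivalent to 85% control only from 20 evaluable upwards, and just below 20 the gap is one to two percentage points. The crude and cumulative-incidence figures are different quantities on different clocks and can disagree about 85%; step 5 shows that this is possible, and no frequency is claimed for it.

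The probabilities rest on independent attrition, no replacement, and LRR independent of attrition. The plan defines evaluability only for toxicity (6.1.1), so evaluable for LRC is taken here to mean a known LRR status at 1 year. It would go too far to call the sample size wrong or the futility stop faulty. The MTD is unaffected.

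**What to change.** - **Section 9.2:** replace the claim to ensure at least 20 with wording such as: to give an expected 20 evaluable at 1 year (about a 71% chance of at least 20 at 15% attrition, without replacement).
- **Section 7.5:** leave the stop at the 4th LRR as it is. State that the 85% hypothesis is judged on 1 minus the cumulative incidence of LRR in all treated patients, by the method in 9.3.2.1.
- **Sections 7.5, 9.1.3 and 9.3.2:** give one time point and one origin, the same in all three, chosen so that the 12-month post-treatment visit is included.
- **If the crude rate is kept for the final judgement:** index the limit to the evaluable number, at most 2 LRRs for 14–19 and at most 3 for 20–24.
- **Study Summary:** name 1-year LRC in place of the unlisted clinical response endpoint.

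These are wording changes and need no extra patients. The cost is that the stated assurance about evaluable numbers becomes less favourable.

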9.3 Data Analyses

9.3.1 Primary endpoint

9.3.1.1 MTD

Acute toxicity will be assessed weekly during treatment and 2 weeks, 1, 2, and 3 months post-treatment to assess for DLT to determine the MTD as outlined in Section 9.1.1.

9.3.2 Secondary endpoints

9.3.2.1 Locoregional control

LRC will be analyzed based on the definition in section 6.2 and estimated using cumulative incidence statistics, with death serving as a competing risk.

9.3.2.2 Progression free survival and overall survival

PFS and OS outcomes will be analyzed based on the definition in section 6.2 and estimated using the Kaplan-Meier method. Survival endpoints will be calculated from the initiation of RT.

9.3.2.3 Physician-reported toxicity

Only adverse events assessed to be definitely, probably, or possibly related to protocol treatment will be considered. The rates of all Grade 3-5 adverse events will be characterized at each time point as outlined in section 5.4.

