1.4.2 Volume de-escalation

Elective nodal volumes for head and neck cancer currently used for intensity-modulated RT (IMRT) is extrapolated from conventional RT fields. Assessment of patterns of failure following IMRT treatments have shown that regional recurrences almost always occur in the high-dose region and solitary failure in the elective volume/dose is rare (15-18). Trials assessing a reduction in the elective nodal volume following induction chemotherapy have shown no solitary elective volume failures (19, 20). More recently, a UT Southwestern Medical Center prospective study of volume de-escalation, where patients with oropharynx cancer received elective dose RT only to the involved and immediately adjacent cervical nodal levels, found no solitary nodal recurrences in

the treated or untreated elective neck volumes, with a minimum follow-up of nearly 2 years (21). Decreasing the volume of elective treatment can improve the toxicity profile of treatment and is currently being incorporated into the standard-of-care arm in large cooperative group trials such as NRG-HN005.

1.4.3 **Hypofractionation**

Cost of oncologic care has continued to increase with efforts in recent years to transition to a value-based care model. In this environment, especially with the implementation of the RO-APM described above, there is an economic rationale to elucidate ways to provide quality care while decreasing resource utilization. Also, there is a strong radiobiological rationale for HFRT in HNSCC to decrease the overall treatment time and thus minimize the effects of accelerated repopulation seen in this disease entity. Accelerated fractionation with its associated decrease in overall treatment time has been shown to improve local control and progression free survival compared to conventional fractionation in HNSCC (22). Effective and safe radiation treatment in a fraction of the time currently required will also improve patient quality of life by decreasing interruptions to their personal and professional lives. Moreover, reducing the overall treatment time may increase completion rates and compliance by reducing the time burden of the therapy. Shortened treatment time will lead to reduced number of weekly cisplatin cycles with concomitant decrease in total cumulative dose, which may also decrease potential chemotherapy side effects such as ototoxicity or nephrotoxicity.

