5.1.3 Demographics

- Age, gender, race

- 5.1.4 Review subject eligibility criteria
- 5.1.5 Review previous and concomitant medications
- 5.1.6 Physical exam including vital signs
 - Temperature, pulse, blood pressure
- 5.1.7 Performance status
 - ECOG Performance status (0-2) or Karnofsky Performance Status (50-100)
- 5.1.8 Adverse event assessment
 - Baseline adverse events will be assessed pre-treatment using CTCAE v5.0. See section 7.2 for adverse event monitoring and reporting.
- 5.1.9 Pregnancy test (for females of child bearing potential)
 - See section 3.1.5.1 for definition
- 5.1.10 Completion of PRO instruments (before start of radiation treatment)
 - MDADI
 - UW-QOL
 - EQ-5D-5L
- 5.1.11 Feeding tube dependence assessment
 - See section 2.3.2 for definition
- 5.1.12 Standard lab work including creatinine
 - Assessment for cisplatin eligibility per medical oncologist

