7.0 ADVERSE EVENTS

7.1 Experimental Therapy

Experimental therapy is de-intensified hypofractionated radiation therapy. Concurrent chemotherapy is considered standard of care.

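### Grade 3-5 toxicity is summarised only for events attributed to an undefined 'protocol treatment', with no any-cause rate beside it, although the endpoint carries no attribution limit

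*Combined protocol and SAP*

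**What the plan says.** **The analysis.** Section 9.3.2.3 states: "Only adverse events assessed to be definitely, probably, or possibly related to protocol treatment will be considered". It continues: "The rates of all Grade 3-5 adverse events will be characterized at each time point as outlined in section 5.4". No threshold, test or comparison is attached.

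**The endpoint.** Sections 2.3.2 and 9.1.3 define rates of grade 3 or higher toxicity, acute (during treatment, 1 and 3 months) and late (6 and 12 months). Neither mentions attribution.

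**What is attributed to what.** The object of attribution changes from place to place:
- 'protocol treatment' in 9.3.2.3;
- 'protocol therapy' in Step 3 of 7.3, and 'study treatment' in the attribution categories under that step;
- 'study therapy' in 7.2;
- RT alone for grade 4 events in the DLT definition in 9.1.1.

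The first four are not defined.

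**Where cisplatin stands.** Section 7.1 says: "Experimental therapy is de-intensified hypofractionated radiation therapy. Concurrent chemotherapy is considered standard of care". The Study Summary, in contrast, gives the regimen as "Hypofractionated intensity modulated radiotherapy with concurrent chemotherapy (weekly cisplatin". Section 1.3 describes the tested treatment as HFRT with weekly cisplatin, 4.4.1 specifies the cisplatin, and 8.1 describes it as the protocol drug.

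**What is collected.** Adverse events are monitored whatever their cause (7.2), attribution is assigned (7.3), and 5.1.8 provides the starting point: "Baseline adverse events will be assessed pre-treatment using CTCAE v5.0".

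**The concern.** The analysis is narrower than the endpoint, and the boundary is a judgement by the treating team in a trial with no blinding and no concurrent control. Two readers could also apply the boundary differently, because the term that sets it is undefined. The attribution scale does not settle the matter: *possible* means that the event may be related and *unlikely* that it may not be. As worded these overlap, and the cut between counted and dropped events runs between them.

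RT is given only with cisplatin here (exclusion 3.2.3 removes patients who cannot receive it), so the toxicity of RT cannot be cleanly separated from that of the regimen. If only the filtered rate is published, nobody can tell whether a low figure reflects tolerability or attribution. The Study Summary names historical chemoradiation as the reference therapy, and the earlier series cited in 1.2 are given without an attribution rule. An informal reading against them would therefore not be like for like.

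**Working it through.** **1. The plan's own figure.** Section 9.2 wants 20 evaluable patients at 1 year with 15% attrition: 20 / (1 - 0.15) = 23.5, rounded up to 24; check, 24 x 0.85 = 20.4. The stated 24 reproduces. No figure is given for the toxicity endpoint, so there is nothing further to reproduce.

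**2. Denominator.** Section 6.2 bases safety analyses on everyone who received any RT fraction: 24 if all are treated, more if patients are replaced under 4.8.

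**3. Direction.** Let x be the number of patients with any grade 3-5 event, and k the number whose only such events are all judged unlikely or unrelated. Then

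- any-cause rate = x/24
- related-only rate = (x - k)/24

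Since k cannot be negative, the related-only rate cannot exceed the any-cause rate. The gap is k/24:

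| k | gap (points) |
|---|---|
| 1 | 4.2 |
| 2 | 8.3 |
| 3 | 12.5 |
| 4 | 16.7 |
| 5 | 20.8 |

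If the denominator at 12 months is 20 patients, each patient is worth 1/20 = 5.0 points.

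**4. Illustration.** The documents give neither x nor k. As assumptions, take any-cause rates near 40% and 60% (24 x 0.40 = 9.6, so 10; 24 x 0.60 = 14.4, so 14), with exact (Clopper-Pearson) 95% intervals:

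| Any-cause | k | Related-only |
|---|---|---|
| 10/24 = 41.7% (22.1-63.4) | 1 | 9/24 = 37.5% (18.8-59.4) |
| | 2 | 8/24 = 33.3% (15.6-55.3) |
| | 5 | 5/24 = 20.8% (7.1-42.2) |
| 14/24 = 58.3% (36.6-77.9) | 1 | 13/24 = 54.2% (32.8-74.4) |
| | 4 | 10/24 = 41.7% (22.1-63.4) |
| | 7 | 7/24 = 29.2% (12.6-51.1) |

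The rows with k = 5 and k = 7 remove half of the affected patients and are extreme cases.

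**5. Which events are exposed.** Mucositis, dermatitis and dysphagia will almost always be at least possibly related to RT, so k is near 0 for them under any definition. If protocol treatment were read as RT alone, the exposed events would be those that 8.1 lists for cisplatin: nausea and vomiting, renal, hearing and blood toxicity. If it includes cisplatin, that route contributes k = 0. What remains is events put down to the tumour, to surgery or to other illness.

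**The case against.** **Cisplatin.** A reader might infer from 7.1 that cisplatin events are dropped. The documents do not support that. Section 7.1 defines *experimental therapy*, which is not the term used in 9.3.2.3. The Study Summary, 1.3, 4.4.1 and 8.1 put cisplatin inside the regimen, 7.1.4 lists reactions to chemoradiotherapy, and Step 4 of 7.3 judges expectedness against the package insert. Where the protocol means RT alone, as in the DLT definition, it says so. This is an ambiguity to close, not a stated exclusion.

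**Direction of error.** A reader might also infer that attribution error always flatters the treatment. That holds only relative to the any-cause count. Against true treatment toxicity, error runs both ways, because a threshold at *possible* also admits events caused by tumour or comorbidity.

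**Hearing and renal benefit.** Section 1.4.3 suggests a shorter course with less cisplatin, "which may also decrease potential chemotherapy side effects such as ototoxicity or nephrotoxicity". It is tempting to say that the filter would manufacture that benefit. The larger limit is ascertainment: the table in 5.4 schedules creatinine only before treatment and no audiometry, and an extra column would not repair that.

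**Which rate should lead.** Objective 2.2.1 concerns toxicities of HFRT, so 9.3.2.3 can fairly be read as making 'toxicity' operational. An any-cause rate would include complications of the salvage surgery or neck dissection in 5.3. This stands, and it argues for showing both rates rather than replacing one.

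**Consequences.** The endpoint is secondary and descriptive. The MTD uses its own DLT definition, and the stopping rules in 7.5 use DLT and locoregional recurrence. Serious events go to the DSMC whether related or not. Feeding-tube and patient-reported outcomes have no attribution filter. All of this stands and limits the weight of the point.

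None of it answers the mismatch between 9.3.2.3 and the endpoint, the missing definition, or the lack of any display of what was removed.

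**Conclusion.** The concern holds as a gap in definition and reporting. Section 9.3.2.3 applies a filter that the endpoint does not have, the filter rests on an undefined term, and no any-cause grade 3-5 summary is planned. The related-only rate is at most the any-cause rate, lower by 4.2 points for each patient removed at n = 24.

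The total size is unknown, since the rates and counts in the tables are assumptions. It is probably modest for the reasons given. With 10/24 any-cause, removing up to four patients (6/24 = 25.0%) still leaves the estimate inside the any-cause interval of 22.1-63.4%. That is no reason to leave it out of sight, because sampling error does not disclose a systematic reduction.

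The documents do not support a claim that severe cisplatin toxicity is excluded, or that dose finding is affected.

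**What to change.** In 9.3.2.3:

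1. At each time point, report the any-cause rate of grade 3-5 events that are new or worse than the baseline grade recorded under 5.1.8, beside the related-only rate, with the number of patients behind each.
2. State that 'protocol treatment' for attribution in this analysis means RT plus concurrent cisplatin, and use one term throughout 7.2, 7.3 and 9.3.2.3. The DLT definition has its own explicit attribution rule and need not change for this purpose.
3. Identify events after salvage surgery or neck dissection separately.
4. State the limits of 'any-cause'. Under 7.2.1, late events come only from radiation oncology, medical oncology and otolaryngology encounters, and only for head and neck or gastrointestinal problems. Under 5.2 and 5.4, weekly on-treatment assessment is a trial procedure only in the escalation phase. Both limits apply equally to the related-only rate.

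**Cost.** One more column and one sentence of definition. Attribution and baseline grades are already collected, and sample size, visits and treatment do not change. The downside is a somewhat higher any-cause figure that includes some events treatment did not cause, which is why the related-only rate stays beside it.
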